3 OBJECTIVES AND OUTCOME MEASURES

3.0 Rutgers Feasibility Study Outcomes

PILOT Objectives	Brief Description/Justification of Outcome Measure	Outcome Measured By	Time Frame
To Determine Patient Willingness to Participate	Willingness to participate is important in determining whether patients would be willing to participate in a large-scale study	Ratio of patients agreeing to participate as compared to all patients asked to participate Thoroughness of consent process and ability to ask questions	Willingness to Participate: Patients – at time of consent by patients Patients – at End-of-Study
To Determine Patient Willingness/Ability to Follow Thru with Triage, Testing and Survey Administration Procedures	Determining willingness and ability to follow thru with triage, testing and survey administration procedures is important for refining the survey procedures	% who complete the study % who complete surveys o Pre-Visit Patient Survey o End-of-Visit Patient Survey % who feel testing (Saliva procedure was easy to comply with o Specimen collection o Specimen preparation for shipping o Specimen storage o Timeliness of results o Reporting of results	% Complete Study: Patients – End-Of-Visit (Day 1) % All Surveys Completed: Patients – End-Of-Visit (Day 1) % Feel Testing Protocol was Easy to Comply With: Patients – End-Of-Visit (Day 1)
To Determine Ease of Use with REDCap Survey Instruments Patient Subject Start-of-Visit Survey End-of-Visit Survey Triage Survey	Determining the ease of use and completeness of the REDCap instruments enables refinement of the system	% who feel surveys are easy to complete due to administration method:	% indicating surveys were easy to complete due to administration method: • Patients – at end of patient visit % indicating survey questions were easy to understand: • Patients – End-Of-Visit (Day 1) % Surveys Completed: • Patients – End-Of-Visit (Day 1)

3.1 Primary Outcomes for Full Study (Data Collection is Being Performed to Determine Instrument Feasibility)

Full Study Objective	Brief Description/Justification of Outcome Measure	Outcome Measured By	Time Frame

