 - headache
 - loss of taste

[figure not shown]
- loss of smell
- sore throat
- congestion or runny nose
- nausea or vomiting
- diarrhea
- At the start of the Dental Visit
 - Undergo a COVID-19 triage screening in the office*
 - Screening includes symptom questions, temperature check, and pulse oximeter reading
- At the End of the Dental Visit
 - Complete two electronic surveys
 - Patient End-of-Visit Survey
 - Questions explore perceptions with testing preferences, PPE observed, environmental controls observed, concerns about returning to dental care, safety precautions valued, importance of triage and testing, likelihood of reporting symptoms, dentists role in COVID-19 testing and vaccinations
 - Patient Participation Survey
 - Questions explore perceptions related to study participation including survey and testing logistics

If any aspect of the COVID-19 triage screening is positive, appointment will be postponed and the participant will be referred to their primary care physician for further testing.

- A Positive screening by reporting one or more symptoms
- A positive temperature is considered greater than 100.4 degrees F
- A positive pulse oximeter is considered when the blood oxygen saturation level is below 95%

The results of the lab processed COVID-19 test will be reported to the Clinic Director or one of the coinvestigators by the lab prior to the scheduled dental visit. Results will be recorded in the *Testing Case Report* form in REDCap.

- If **POSITVE**: The Clinic Director or one of the co-investigators will communicate positive results to the participant upon receipt. Positive participants will be instructed to consult with their primary care provider for further testing.
- If NEGATIVE: The Clinic Director or one of the co-investigators will communicate negative results to
 the participant by phone on the day prior to the dental visit after the COVID-19 triage screening is
 performed.

Methods for Data Collection

REDCap will be used to collect and maintain all study data. For all surveys and case reports, the Research Clinical Director or co-investigator will enter data directly into REDCap. Surveys will be entered by the patient with the Clinical Director or co-investigator's assistance.

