7 STUDY PROCEDURES/EVALUATIONS

As part of this study, COVID-19 triage case report will be completed, COVID-19 testing will be performed and perception and attitude surveys will be administered. During day 1, the dental visit, normal patient care will be provided to the patient subject.

For the purpose of this study, a COVID-19 positive result is not considered an adverse event though results of this test will be recorded.

Patient subjects who are COVID-19 antigen or viral positive or who triage positive without any preexisting medical condition, will not be seen for their scheduled dental visit. The subject will be referred to their physician for a definitive diagnosis and follow-up. The follow-up call will be made 1 week after (and 2 weeks after if necessary,) learning of the research study protocol call viral or antigen positive test results to record any confirmatory tests which were obtained based upon the advice of the worker's physician. The dental visit will be rescheduled once the subject has fully recovered. In the event of a dental emergency, care will be rendered via tele dentistry or referral to University Hospital Unit 1 (Oral and Maxillofacial Surgery/Dental Medicine Clinic) via University Hospital's Emergency Room.

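### Participants postponed for a positive test or triage screen who do not return give no testing ratings, and the plan contradicts itself on when those ratings are collected and who is postponed

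*Combined protocol and SAP*

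**What the plan says.** Section 3.0 lists the testing-ease outcome with the time frame "Feel Testing Protocol was Easy to Comply With: Patients – End-Of-Visit (Day 1". The rated items are specimen collection, preparation for shipping, storage, timeliness of results and reporting of results.

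Section 4 gives two surveys at the end of the dental visit. The Patient Participation Survey carries the testing items: "Questions explore perceptions related to study participation including survey and testing logistics". The End-of-Visit Survey depends on having been in the clinic: "Questions explore perceptions with testing preferences, PPE observed, environmental controls observed".

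On postponement, section 4 states: "If any aspect of the COVID-19 triage screening is positive, appointment will be postponed". Section 7 applies it to those who test positive and to those "who triage positive without any preexisting medical condition, will not be seen for their scheduled dental visit". It then adds: "The dental visit will be rescheduled once the subject has fully recovered". It also schedules a call one week after a positive test, and a second at two weeks if needed, to record confirmatory testing.

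On results, section 4 has staff "communicate positive results to the participant upon receipt", whereas a negative result is given to "the participant by phone on the day prior to the dental visit", after the triage screen.

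The section 7.1 table puts the Patient Participation Questionnaire at End of Study, Day 28. Sections 4 and 6.1 and Appendix A put it at the Day 1 visit.

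**The concern.** The ratings of the testing procedure are tied to a visit that a positive test or triage screen takes off the calendar. Section 7 reschedules the dental visit. It gives no route for the testing ratings of someone who never attends the new date, and its follow-up calls are not described as collecting them.

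Two of the five rated items, timeliness and reporting, concern how the result reached the participant, and that route depends on the result. If test-positive participants do not return, both items are answered only by people told of a negative result by phone. A feasibility study meant to refine testing logistics would then have no patient view of how positive results are delivered. Enrolling more participants would not fill that gap if those who test positive still went unrated.

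**Working it through.** The plan states no power, precision or sample-size figure, so there is nothing to reproduce. The inputs are:

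- N = 20 (section 5.3; the Protocol Summary says up to twenty).
- No sample-size calculation (section 11.2).
- Frequencies only, with no stated denominator or rule for missing ratings (section 11.3).
- No postponement rate and no return rate anywhere.

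**Who goes unrated.** Postponed participants who attend the rescheduled visit can be rated there. The unrated group, of size k, is those who are postponed and do not return. It can include test-positive and triage-positive participants. Only the test-positive ones remove the positive-result route, because section 4 states no exception to the phone call for a triage-positive participant with a negative test.

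**Effect on a percentage over all 20.** If e participants rate testing easy and k are unrated, the figure for all 20 lies between e/20 and (e + k)/20. The width is k/20, whatever e is.

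| k | Width (k/20) | If every rated participant says easy: reported | Lowest value over all 20, (20 − k)/20 |
|---|---|---|---|
| 1 | 5 points | 100% | 95% |
| 2 | 10 points | 100% | 90% |
| 3 | 15 points | 100% | 85% |
| 4 | 20 points | 100% | 80% |

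For example, with k = 2 and 16 of 18 rating testing easy, the reported figure is 16/18 = 88.9%. Over all 20 it lies between 16/20 = 80% and 18/20 = 90%.

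**Against sampling noise.** The exact (Clopper-Pearson) 95% interval for 16 of 20 runs from 56.3% to 94.3%. Shifts of 5 to 10 points sit well inside it.

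**How likely a postponement is (assumption only).** If each participant were postponed independently with probability p, the chance of at least one postponement among 20 is 1 − (1 − p)^20:

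- p = 2%: 33%
- p = 5%: 64%
- p = 10%: 88%
- p = 20%: 99%

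The expected numbers postponed (20p) are 0.4, 1, 2 and 4. These count postponements; k is smaller to the extent that people return.

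**The two contradictions.**

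- Questionnaire timing: Day 28 in section 7.1 against Day 1 in sections 4 and 6.1 and Appendix A, a difference of 28 − 1 = 27 days. Under Day 28 the testing items would no longer depend on attending the visit, and much of the gap would close. Under Day 1 it stays open.
- Who is postponed: section 4 postpones on any positive element of triage. Section 7 limits this to triage-positive participants with no pre-existing medical condition. The two rules give different sets of postponed participants.

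**The case against.** The best reply is that the end-of-visit surveys are tied to the end of the dental visit, so a rescheduled visit brings them with it. Test-positive participants also stay in contact through the follow-up calls, and the Day 28 entry may be meant to separate the questionnaire from the visit. Most of this stands. It does not cover someone who fails to return. The calls are given a different purpose and apply only after a positive test. Nothing reserves Day 28 for postponed participants.

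A reader might infer several stronger points, which the documents do not support:

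- *That postponed participants are left out by design.* The visit is rescheduled, and the natural reading makes it the new Day 1. The specimen window in section 6.1 raises the question of repeating earlier steps, not of who gives ratings.
- *That positive results reach participants days sooner than negative ones.* Section 7.2.2 says results normally take up to a week, so a positive result may arrive no earlier than the day-prior call. Only the difference in route is shown.
- *That counting protocol stops as non-completion distorts the completion percentage.* The objective in section 3.0 covers ability as well as willingness, so an all-cause figure fits it.
- *That unopened surveys would go uncounted.* Section 11.3 records completeness as Yes/No, and an unopened survey is a No.
- *That the section 5.2 exclusion bars a return.* A postponed participant is still in the same enrolment.
- *That postponed participants forfeit the $100.* Section 5.3 is silent on postponement. That is missing detail, and the consent form, not available here, may settle it.

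**Conclusion.** The point holds as a minor one. The plan gives no way to obtain testing ratings from a postponed participant who does not return. If the test-positive participants are the ones missing, the timeliness and reporting items describe the negative route only. The size is 5 points of uncertainty per unrated participant at N = 20, within sampling noise for one or two people. The issue is therefore which experience goes unrated, not precision.

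This rests on reading the rescheduled visit as Day 1 and on at least one postponed participant not returning; the documents give no rate for either step. The two contradictions, on questionnaire timing and on who is postponed, stand on the text alone and need reconciling whatever the numbers turn out to be.

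**What to change.** 1. Keep the in-office Day 1 administration for participants seen as scheduled. For postponed participants only, give the Patient Participation Questionnaire once, by REDCap link or (after a positive test) at the section 7 follow-up call, after any test result has been given. Give the End-of-Visit Survey at the rescheduled visit, since it asks about what was seen in the clinic. Report each rating with the numbers enrolled, tested, postponed and rated, and flag ratings collected remotely.
2. Reconcile Day 28 in section 7.1 with Day 1 in sections 4 and 6.1 and Appendix A. Reconcile sections 4 and 7 on who is postponed; this review does not choose the rule.

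The cost is a short amendment and one remote link. The downside is a different mode of administration for a few participants. Ease due to administration method is itself an outcome in sections 3.0 and 11.3, which is why the link should not go to everyone and why remote ratings should be flagged. Postponed participants will not yet have seen the End-of-Visit Survey, so any item about it should be marked not applicable for them.

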4 STUDY DESIGN

Description: This study will assess the feasibility of implementing one COVID-related testing procedure in the dental setting. Results from this study may provide preliminary data to inform a larger network-wide study grant application.

Study Population: The study population for this study will be patients seen at the Rutgers School of Dental Medicine.

Important Outcomes: For this study, important outcomes include percent of patients willing to participate and percent completing the protocol.

Single or Multicenter: Single- this study will utilize the Rutgers School of Dental Medicine's Newark facility.

Number of Study Groups/Arms: One (1)

Expected Duration of Subject Participation: Subjects will be actively participating in the study for 2 weeks.

Sequence of Procedures and Duration of Study Period: Consent Process

About two weeks prior to their scheduled dental visit, patients will be contacted by the dental office to determine their willingness to participate in the study. Patients who indicate interest will be sent an email link, which opens the consent. The consent will clearly outline participant expectations and offer the opportunity for potential participants to contact the office for more information as needed. Participants who fully understand the study and elect to participate will affirm their willingness to participate by clicking the "I agree to take part in this study" button at the end of the consent form. Once in the office to provide their saliva sample, patients will also be asked to provide signed informed consent.

Study Procedures

Study participants will be asked to do the following:

- Two weeks before the dental visit
 - o Complete an electronic survey: Patient Pre-Visit Survey
 - Questions explore perceptions of safety and comfort, reasons for delaying dental care, concerns about returning to dental care, safety precautions valued, importance of triage and testing, and demographics
 - Launched automatically after the completed consent
 - Receive a saliva collection kit by mail
- One week before the dental visit
 - o Complete a COVID-19 saliva test
 - Spit into a tube
 - Package as directed
 - Drop off the completed test kit at the dentist's office
- Day prior to the dental visit
 - Undergo a COVID-19 triage screening over the phone*
 - Screening includes symptom questions (presence or absence of):
 - fever or chills
 - cough
 - shortness of breath or difficulty breathing
 - fatigue
 - muscle and body aches
 - headache
 - loss of taste

[figure not shown]
- loss of smell
- sore throat
- congestion or runny nose
- nausea or vomiting
- diarrhea
- At the start of the Dental Visit
 - Undergo a COVID-19 triage screening in the office*
 - Screening includes symptom questions, temperature check, and pulse oximeter reading
- At the End of the Dental Visit
 - Complete two electronic surveys
 - Patient End-of-Visit Survey
 - Questions explore perceptions with testing preferences, PPE observed, environmental controls observed, concerns about returning to dental care, safety precautions valued, importance of triage and testing, likelihood of reporting symptoms, dentists role in COVID-19 testing and vaccinations
 - Patient Participation Survey
 - Questions explore perceptions related to study participation including survey and testing logistics

If any aspect of the COVID-19 triage screening is positive, appointment will be postponed and the participant will be referred to their primary care physician for further testing.

- A Positive screening by reporting one or more symptoms
- A positive temperature is considered greater than 100.4 degrees F
- A positive pulse oximeter is considered when the blood oxygen saturation level is below 95%

The results of the lab processed COVID-19 test will be reported to the Clinic Director or one of the coinvestigators by the lab prior to the scheduled dental visit. Results will be recorded in the *Testing Case Report* form in REDCap.

- If **POSITVE**: The Clinic Director or one of the co-investigators will communicate positive results to the participant upon receipt. Positive participants will be instructed to consult with their primary care provider for further testing.
- If NEGATIVE: The Clinic Director or one of the co-investigators will communicate negative results to
 the participant by phone on the day prior to the dental visit after the COVID-19 triage screening is
 performed.

Methods for Data Collection

REDCap will be used to collect and maintain all study data. For all surveys and case reports, the Research Clinical Director or co-investigator will enter data directly into REDCap. Surveys will be entered by the patient with the Clinical Director or co-investigator's assistance.

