2.3 Rationale

2.3.1 Potential Risks

This research involves testing procedures with varying degrees of risk to the study participants.

• Saliva Test- minimal risk. The saliva test is non-invasive, requires spitting into a tube, and is completed independently, without interaction with a member of the healthcare team.

In addition, different COVID-19 test types have varying degrees of sensitivity and specificity, which may result in false negative and false positive test results. While a false negative result may give a participant a false sense of security, this would not pose additional risks to patients or the DHCWs in the dental practice, as the patient would have been treated according to the office's infection control protocol regardless of participation in the study. On the other hand, a false positive result will prompt the patient to undergo additional testing by their primary health care provider. Should they test positive again, they would need to follow their local health department recommendations which may require quarantine.

There is a risk of loss of confidentiality for all study participants. Precautions will be in place to minimize this risk, such as collecting only minimal identifying information, using unique study codes for participants,

collecting data using encrypted computers, and maintaining electronic data files on a password-protected computer drive, and storing data on encrypted computers or in locked cabinets (located in locked offices). Individual identifier numbers that are linked to participant contact information will be stored separately from the data. Compliance with all IRB regulations concerning data collection, data analysis, data storage, and data destruction will be strictly observed.

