6 STUDY SCHEDULE

6.1 Patient Subjects

The following is the schedule of events for patients participating in the study.

Visit	Day	LAB Subjects Activities Performed
2 Weeks Prior	Day -14 (+/- 7 days)	Potential subjects contacted to introduce and determine interest in the study Obtain electronic consent Complete Pre-Visit Patient Survey
1 Week Prior	Day -7 (+/- 5 days)	Obtain informed consent signatures Provide saliva specimen
Day Prior	Day -2 (+/- 3 days)	Perform Prior-Day Triage Survey Obtain test results and provide to patient subject
Visit	Day 1	Complete Start-of-Visit Survey Complete Start-of-Visit Triage Case Report (Provision of Dental Treatment - not part of research protocol) Complete End-of-Visit Survey Complete Patient Participation Questionnaire

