7.2 Laboratory Procedures/Evaluations

7.2.1 Clinical Laboratory Evaluations

Patient subjects will be tested for COVID-19 using a lab-processed saliva test.

	Patient LAB Test (PCR Viral Test)	
Test Description		
Company	Rutgers	
Sample collected via	Saliva collection tube with buffer	
What is being Tested	SARS-CoV-2 RNA	
Test Administration	Saliva collection performed by subject with saliva collection tube provided by a Research Clinical Director	
(specimen collection)		
Test Administration	RT-PCR test performed at ICPH-PHRI center, New Jersey Medical School, Newark, NJ	
(specimen processing)		
Results	Dichotomous (+ or -)	

With regard to the quality of the COVID-19 test specimen, the following will be used to assess the quality of the specimen.

	LAB Test
Indication of Proper	Accurate Diagnostic Labs will report if a sample is not able to be processed. This feedback will be used to identify insufficient
Processing	training or unanticipated problems.

Compliance with study protocols will be based upon the PI and the Chief of Clinical Protocol following the REDCap dashboard. The dashboard exhibits red indicators for instruments which have been started and not completed, yellow indicators for instruments which have been completed and not verified and green indicators for instruments which have been completed and reviewed. The PI or Chief of Clinical Protocol will be responsible for reviewing each instrument and changing the status from unverified to verified. Any issues with compliance with the study protocol identified by the PI or Chief of Clinical Protocol will be reviewed with the Research Clinical Director and be used to identify any unanticipated problems and develop/implement any necessary corrective action plans.

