7.2.2 Specimen Preparation, Handling, and Storage

The following details specimen preparation, handling and storage.

	LAB Test
	LAD 165t
Sample Collection & Shipping	
Sample Collection Materials	Spectrum Saliva collection system via Accurate Diagnostics
Storage of Specimen Collection Supplies and POC	Clinical Research Center (D level of Dental School) and dental clinic dispensaries in the dental school
Test Kits	
Transport Media	Buffer solution
Packaging Specimen for Shipping	Sealed biohazard plastic bag
Sample Processing (Performing the Test)	
Processing Supplies	RNA extraction, followed by RT-PCR
Processing Time	About four hours
Conditions for Stability and Transport	
Condition	
Stability prior to Use	No special storage conditions required
Stability during shipping	Yes due to transport media
Storage prior to processing	PHRI Laboratory
Stability prior to processing	Stable at room temperature
Tracking	
Labeling	Specimen ID (bar code)
	Subject ID (bar code)

	Subject Name
	Date of Specimen
Tracking of Specimen Collection Kits	REDCap System and/or Excel Worksheet
Tracking of Tests Administered	Completion of REDCap COVID-19 Test Order and Results Form (which enables the generation of a
	Specimen Tracking Log)
Reporting of Results	
Time from specimen collection to reporting of	Results are normally available within 1 week
results	
Results Reporting	Via secure e-mail and then posted into REDCap via Research Clinical Director

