7.2.3 Specimen Shipment

Saliva and immediately placed into a preservative and the tube with the sample then placed into a biohazard bag.

	LAB Test
Shipment Method and Frequency	Samples will be obtained from subjects Monday thru Thursdays. Saliva samples will be placed into the
	pick-box located on the B level of the MSB building.)
Packaging Specimen for Shipping	Sealed plastic biohazard bag
Shipping Address	Accurate Diagnostic Labs
	[name]
	[name]
Contact Information for Laboratory Personnel	Accurate Diagnostic Labs
	[contact]
Days and Times shipments are allowed	Monday thru Friday
	9:00 am to 5:00 pm
Labeling Requirements for Specimen Shipping	Subject Number, Subject Name, Birth Date and Collection Tube ID/Bar Code
Special Instruction for Specimen Collection	Subject should not eat or drink for 30 minutes prior to saliva specimen collection
Special Instructions for Specimens for Shipment	No special instructions
(i.e. dry ice, wet ice)	
Completion of Specimen-Tracking Log	Completion of REDCap COVID-19 Test Order and Results Form (which enables the generation of a
	Specimen Tracking Log)

9/1/2023

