11.3 Final Analysis Plan

Data to be collected includes:

Item	Type of Variable
Willingness to Participate	 Willingness to participate (Binary – Yes/No)
Patient willingness to participate	
Triage Survey	Ease of Administration (3 point Likert Scale) Very easy to complete survey due to administration method Easy to administer complete survey due to administration method Not easy to complete survey due to survey administration method Completeness (Binary – Yes/No) Question understandability (3 point Likert Scale) Very clear to understand Understandable with some clarification provided by the administrator Not clear to understand
Safety Perception Survey	
Start-of-Visit Patient Survey End-of-Visit Patient Survey	Administration method (3 point Likert Scale) Very easy to complete survey due to administration method Easy to complete survey due to administration method Not easy to complete survey due to administration method
	 Completeness (Binary – Yes/No)
	 Question understandability (3 point Likert Scale) Very clear to understand Understandable with some clarification provided by the administrator Not clear to understand
Testing Logistics	Specimen Collection (3 point Likert Scale)
LAB – saliva SARS-CoV-2 viral test	 Very easy to collect Easy to collect Not easy to collect Specimen preparation for shipping (3 point Likert Scale) Very easy to prepare Easy to prepare Not easy to prepare Specimen storage (Binary – Easy/Not Easy) Easy to Store Not easy to store

	Timeliness of results (3 point Likert Scale) Very timeless access to results Timely access to results Access to results not timely Reporting of results (3 point Likert Scale) Very easy to access results Easy to access results Not easy to access results	
Testing Case Report	 Completeness (Binary – Yes/No) 	

Descriptive statistics (frequencies) for all variables will be analyzed.

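### The specimen window runs to Day -2, too late for a one-week turnaround to deliver the saliva result before the Day 1 visit as Section 4 states

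*Combined protocol and SAP*

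**What the plan says.** Section 4 has the laboratory report each result to the Clinic Director or "one of the coinvestigators by the lab prior to the scheduled dental visit". It then gives two branches. A positive result is passed on when it is received. A negative result is given by phone on the day before the visit, after the triage call.

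The timing comes from other sections:

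- Section 4 sets the saliva test at one week before the visit. Section 6.1 and Appendix A widen this to Day -7 +/- 5 days, and 7.1 uses the same window for the consent signature taken when the specimen is brought in. The visit is Day 1.
- The time from specimen collection to reporting is in 7.2.2: "Results are normally available within 1 week". The same table separately gives a processing time of about four hours.
- The Day Prior row of 6.1 includes "Obtain test results and provide to patient subject".
- On failed samples, 7.2.1 says "Accurate Diagnostic Labs will report if a sample is not able to be processed". It uses that report to find training gaps or unanticipated problems.
- Section 7 says that viral-positive or triage-positive patients "will not be seen for their scheduled dental visit".

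No section says what to do with a participant who has no result when the visit comes round.

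**The concern.** Section 4 treats a result before the visit as something the schedule delivers. The specimen window and the stated turnaround, each taken at face value, do not deliver it. Staff can collect on a permitted day, the laboratory can report within its normal time, and the result can still arrive after the patient has been treated. No window is breached and no deviation is recorded.

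Two things are at stake. First, a participant can reach the visit with no result, and the plan does not say whether to proceed or postpone, so staff would decide case by case. Second, Section 4 names the percentage completing the protocol as an important outcome. With 20 participants each person moves that percentage by 5 points (1/20), so unwritten postponement decisions could show in it. Refining logistics is the stated purpose of this pilot, so a schedule that conflicts with its own requirement is worth correcting before it is carried into a larger study.

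**Working it through.** The plan gives no figure for this, so there is none to reproduce. The check is calendar arithmetic.

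**Inputs.** Specimen day s runs from -7 - 5 = -12 to -7 + 5 = -2, which is 11 days (6.1, Appendix A). The visit is Day 1 (6.1). Turnaround T is normally up to 7 days (7.2.2). The documents do not say whether the calendar has a Day 0, so both cases are shown.

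**Formula.** Days from specimen to visit: k = 1 - s with a Day 0, and k = -s without. For s = -12 to -2 this gives k = 13 down to 3, or 12 down to 2. The result arrives T - k days after the visit; a negative value means before it.

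**At T = 7:**

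| Specimen day | Reports on (with Day 0) | Relative to visit | Reports on (no Day 0) | Relative to visit |
|---|---|---|---|---|
| -12 to -9 | Day -5 to -2 | before | Day -5 to -2 | before |
| -8 | Day -1 | 2 before | Day -1 | 1 before |
| -7 | Day 0 | 1 before | Day 1 | visit day |
| -6 | Day 1 | visit day | Day 2 | 1 after |
| -5 | Day 2 | 1 after | Day 3 | 2 after |
| -4 | Day 3 | 2 after | Day 4 | 3 after |
| -3 | Day 4 | 3 after | Day 5 | 4 after |
| -2 | Day 5 | 4 after | Day 6 | 5 after |

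So 4 of 11 specimen days (with a Day 0) or 5 of 11 (without) report after the visit day. Counting the visit day as well, 5 of 11 or 6 of 11 do not report on an earlier day.

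**Other turnarounds.** The latest specimen (Day -2) reports after the visit by T - 3 days with a Day 0, or T - 2 without:

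- T = 2: not after the visit day in either case
- T = 3: 0 or 1 day
- T = 5: 2 or 3 days
- T = 7: 4 or 5 days

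**At the Day -7 target.** k = 8 or 7, so a turnaround of up to 7 days never reports after the visit day. Without a Day 0, a full 7 days lands on the visit day itself.

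**Last safe specimen day.** To report at least one day before the visit, T must be no more than k - 1. With a Day 0 this gives s no later than -T; without, no later than -(T + 1). For T = 7 that is Day -7 or Day -8.

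**The case against.** The strongest reply is that this seldom bites. Section 4 aims for one week before the visit, bench processing takes about four hours, and real turnaround may be well under a week. That stands as far as frequency goes, but it does not remove the conflict: 7.2.2 states the collection-to-report time separately from processing time, and the word normally sets no maximum.

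Four stronger readings are tempting, and the documents support none of them.

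- **That a sizeable share of participants would be treated before their result.** Any percentage depends on an assumed spread of specimen days and turnaround. With both even (turnaround 1 to 7 days), 10/77 = 13.0% (with a Day 0) or 15/77 = 19.5% (without) arrive after the visit day. Weighting specimen days in a triangle around Day -7 (weights 1 to 6 to 1, total 36) gives 20/252 = 7.9% or 35/252 = 13.9%. An even spread with turnaround 1 to 3 days gives 0/33 = 0% or 1/33 = 3.0%. The documents give no basis for choosing among these. Monday-to-Thursday collection (7.2.3) does not settle it either.
- **That treating someone whose positive result is pending would breach Section 7.** The bar there reads most naturally as applying to known positives, since its follow-up call is timed from learning the result. Section 2.3.1 also notes, for false negatives, that patients are treated under the office's "infection control protocol regardless of participation in the study". Late positives would be few: if 2 to 5% of participants were positive (an assumption), the even-spread count of 2.6 to 3.9 late results in 20 implies about 0.05 to 0.2 late positives, before triage removes any with symptoms.
- **That missing results would go unrecorded.** Section 11.3 tabulates Testing Case Report completeness, 7.1 schedules that form for the day prior, and Section 13 treats incomplete forms as an outcome. A participant still waiting could also choose "Not easy to access results" or the not-timely option. What these do not show is whether a result arrived before or after the visit.
- **That the results contact could precede the specimen because the windows overlap.** The steps are ordered, so this is over-literal. The +/- 3 days in 6.1 against +/- 2 days in 7.1 and Appendix A is clerical.

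**Conclusion.** The point holds as an internal conflict. The specimen window is too wide for the stated turnaround if the result is to precede the visit. At 7 days, 4 or 5 of the 11 permitted specimen days report after the visit day, by at most 4 or 5 days; the two figures differ only in whether a Day 0 exists. This rests on the windows as written and on a turnaround at the top of the stated normal range.

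The frequency is not known and should not be quoted as a percentage. The safety consequence is small, given a phone triage, a visit-day triage with temperature and oximetry, and usual infection control. The missing instruction for a pending or unprocessable result is a gap in detail, to be closed along with the window.

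**What to change.** Set the last specimen day from the laboratory's turnaround T: Day -T if the calendar has a Day 0, or Day -(T + 1) if not, and say which numbering applies. For the stated 7 days this is Day -7 or Day -8. If the laboratory confirms a shorter time the limit can move later: 5 days gives Day -5 or -6, and 3 days gives Day -3 or -4. The Day -7 target survives any T up to 6 days under either numbering. Use the same limit in 6.1, 7.1 and Appendix A.

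Along with this:

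- Add a line to Section 4 saying whether a participant whose result is pending or unprocessable at the day-prior call is postponed, or is seen under usual infection control and told the result on receipt. This is needed even with a tighter window, because turnaround has no stated maximum and samples can fail.
- Report the number of results in hand before the visit.

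The cost is a narrower collection window and possibly a few specimens or visits rescheduled. At T = 7 the 11 days shrink to 6 (Day -12 to -7) or 5 (Day -12 to -8). Section 7.2.3 adds "Samples will be obtained from subjects Monday thru Thursdays", so those 6 consecutive days contain at least 3 collection days and those 5 at least 2. If postponement is chosen, it may lower the completion percentage slightly, but by a written rule.
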